12. BIOMARKER AND IMMUNOGENICITY ANALYSIS

Biomarker data, e.g. P-selectin, will be summarized for each time point using descriptive statistics (number of subjects, mean, SD, median, minimum, and maximum). A listing will be presented by subject.

The PB2452 antibodies will be summarized by visit and treatment. A listing for subjects will also be provided by treatment and visit.

If positive ADA is observed, results may be reported by ADA status for AEs, efficacy and pharmacokinetics. An ADA-positive subject is defined as a subject with at least one ADA-positive sample at any time during the treatment or follow-up observation period. In case of a positive pre-treatment sample, if the titer of at least one post-treatment ADA is elevated at least 2 folds of the titer in pre-treatment sample, this subject is also ADA positive. In all other cases, a subject is considered negative for ADA.

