2.1.4 Supportive Clinical Data

The first-in-human Phase 1 study (PB2452-PT-CL-0001) has been clinically completed, the database is locked, and final analyses are complete with the exception of exploratory endpoints. The safety, PK, and PD data described herein will be incorporated into a clinical study report. This study was a single-center, randomized, double-blind, placebo-controlled, single ascending dose study to evaluate the safety, tolerability, PK, and PD of PB2452 with and without ticagrelor pretreatment in healthy male and female subjects ages 18-50 years. Ten sequential dose cohorts were evaluated. Cohorts 1, 2, and 3 assessed 30 min IV infusions of PB2452 without ticagrelor pretreatment while Cohorts 4-10 assessed IV infusion duration-dependent reversal of the antiplatelet effects of ticagrelor. Detailed descriptions of the clinical safety, PK, and PD profiles of PB2452 may be found in the IB for PB2452.

PB2452 appeared generally safe and well tolerated across a dose range of 0.1 g to 18 g. A total of 30 adverse events occurred after initiation of PB2452 or placebo and were reported by 19 of the 64 volunteers (30%). Of the 48 volunteers who received PB2452, 17 (35%) reported 27 adverse events; of the 16 volunteers who received placebo, 2 (12%) reported 3 adverse events. There were no dose-limiting toxic effects or infusion-related reactions (IRRs). There were no deaths or adverse events that led to discontinuation of the trial drug. Of the 48 volunteers who received PB2452, 21 (44%) had detectable anti-drug antibodies in blood obtained 7 and/or 28 days after exposure; 15 (31%) had been positive before they received PB2452 and 6 (12%) became positive after they received PB2452, albeit with low titers of 40 (in 5 volunteers) and 160 (in 1 volunteer). Of the 16 volunteers who received placebo, 3 (19%) were positive for anti-drug antibodies, with 2 (12%) having preexisting antibodies. The presence of these antibodies had no observed effect on the safety or efficacy of PB2452 (Bhatt DL, 2019).

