2.1.4.1 Clinical Pharmacology and Pharmacokinetics

The PK profile of PB2452 demonstrated that mean plasma concentrations of PB2452 rapidly declined following the end of infusion across all cohorts. In cohorts 1-3 when PB2452 was administered as a 30-minute intravenous infusion in the absence of ticagrelor, elimination appeared to be biphasic with half-life values ranging from 1.5 to 9.2 hours for the dose range 0.1 g to 1 g. In the presence and absence of ticagrelor, geometric mean observed maximum plasma concentration (C_{max}) values and geometric mean area under the plasma concentration versus time curve (AUC) values of total PB2452 from time zero extrapolated to infinity (AUC_{0-∞}) appeared to increase in a dose-proportional manner. The inter-individual variability (geometric mean coefficient of variation [CV%]) for C_{max} and AUC_{0-∞} was low, ranging from 4.8% to 28.9% across Cohorts 1-3.

Clinical Study Protocol PB2452-PT-CL-0003-Phase 2b Version 2 dated 28May2021

PB2452 produced an increase in the mean total plasma concentrations of ticagrelor and TAM compared to placebo, and this effect was dependent upon the dose of PB2452. Among volunteers who received placebo and ticagrelor pretreatment, the mean AUC_{0–48} for ticagrelor ranged from 4730 to 6750 hours times nanograms per milliliter. Among volunteers who received 30-minute infusions of PB2452 and ticagrelor pretreatment, there was a dose-dependent increase in mean AUC _{0–48} for ticagrelor by a factor of 2.0 to 5.6. Among volunteers who received 18 g of PB2452 with longer infusions and ticagrelor pretreatment, the mean AUC _{0–48} for ticagrelor was increased by a factor of 5.6. This increased ticagrelor exposure probably reflected tight binding between PB2452 and ticagrelor and redistribution of extravascular ticagrelor into the vascular compartment.

Ticagrelor and TAM are known to be primarily metabolized hepatically with less than 1% of the dose cleared renally (BRILINTA (ticagrelor), 2021). As expected, PB2452 increased the renal clearance of ticagrelor and TAM in a dose-dependent manner presumably reflecting the clearance of PB2452 complexed with ticagrelor and TAM via the kidney. This is consistent with the preclinical PK data (Section 2.1.3.3) and is also consistent with the prediction that PB2452 changes the primary route of ticagrelor elimination from hepatic to renal.

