2.1.5.1 Additional Risks

PB2452 lacks an endogenous target, and in a human tissue panel cross-reactivity study utilizing PB2452-FITC, no staining was observed in any of the human tissues on the panel. Therefore, due to high binding specificity, the risk of off-target effects is considered low.

The 14-day extended single-dose non-clinical GLP toxicology study conducted in rats with PB2452 doses up to 2000 mg/kg did not identify a clinically relevant safety concern. The maximum human dose proposed for Phase 1 was approximately 250 mg/kg.

Potential risks based on class effects

• Infusion site reactions:

Possible risks associated with IV administration are redness, swelling, pain, induration, and sometimes infection at the administration site

• Anaphylactic-type and infusion reactions:

Although anaphylactic-type reactions are considered of importance due to their serious nature, they are rare. Acute anaphylactic reactions may include cardio-respiratory distress, chest pain, hypotension, dyspnea, bronchospasm, respiratory failure, urticaria, pruritus, angioedema, nausea, vomiting, diarrhea, hypotonia, and collapse

• Immunogenicity:

Development of antibodies to PB2452 might pose issues with a subsequent dose of PB2452, either an amnestic immunological reaction or, in the case of neutralizing antibodies, reduced efficacy. However, it is considered very unlikely that readministration will be required

• Thrombosis:

There is a risk of thrombosis following reversal of ticagrelor's therapeutic antiplatelet effect in patients with clinical conditions at very high risk of thrombosis, such as recent ACS or recent placement of a coronary stent

• Bleeding (aspirin and/or ticagrelor only):

Volunteers receiving pre-treatment with both aspirin and ticagrelor have a risk of bleeding during the clinical study

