6 STUDY CONDUCT

The Investigator will agree to perform all aspects of this study in accordance with the ethical principles that have their origin in the Declaration of Helsinki, ICH E6(R2): GCP, the protocol, and all national, state, and local laws or regulations.

This Phase 2B study will consist of:

- A Screening period (Days -45 to -4)
- Pretreatment with ASA 81mg daily (Day -7 to Day 1)
- Check-in Day–admission to study clinic (Day -3 to Day 3)
- Pretreatment and ticagrelor treatment (Day -2 to Day 1)
- On-site Randomization/Treatment (Day 1)
- 2-Day on-site Follow-up period (Day 1 to Day 3)
- Day 7 Follow-up visit (Day 7)
- Final Follow-up visit on (Day 35+3)

Plasma samples for PD and PK analysis of PB2452, ticagrelor and its active metabolite, (TAM) will be collected at Day -2, pre-dose (within 10 minutes prior to start of infusion), Day 1 and Day 2 at 5, 10 and 30 minutes and 1, 2, 4, 8, 12, 20, 24, 36, 48 hours following initiation of the study drug infusion. Plasma PK samples will also be collected on Day 7, and Day 35±3 after initiation of study drug infusion.

Safety and tolerability will be carefully monitored through the study. The existence of anti-drugantibodies will be assessed in all subjects at Day -3, Day 1 (randomization), Day 7 and 35 ± 3 following administration of study drug at 3 months and then every 6 months until return to baseline.

The estimated duration of the study for each subject, excluding screening, is approximately 35 ± 3 days.

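### The optional split of results by ADA status in SAP 12 counts antibody first detected at Day 7 or Day 35, so for 4-hour efficacy and early PK it dilutes any effect of antibody present at dosing

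*SAP*

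**What the plan says.** SAP 12 provides: "If positive ADA is observed, results may be reported by ADA status for AEs, efficacy and pharmacokinetics". Protocol 9.3.8 gives the same option without defining the status. SAP 12 then defines an ADA-positive subject as one with "at least one ADA-positive sample at any time during the treatment or follow-up observation period". For a subject already positive before treatment it adds a second rule, "if the titer of at least one post-treatment ADA is elevated at least 2 folds of the titer in pre-treatment sample", under which that subject is positive too. Everyone else is negative. ADA is also to be summarized by visit and treatment, and listed.

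Protocol 6 says that ADA "will be assessed in all subjects at Day -3, Day 1 (randomization), Day 7 and 35". Footnote s to the Schedule of Events (Protocol 1.1) requires the Day 1 sample before the infusion starts, so the first scheduled post-dose sample is Day 7. The primary endpoint (SAP 9.1) and the hierarchically tested secondary endpoints (SAP 9.2) cover the first 4 hours after the start of study drug.

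**The concern.** Grouping a 4-hour outcome by a status that can be acquired on Day 7 or Day 35 puts the grouping event after the outcome. Antibody first formed after the infusion cannot have altered PRU or PRI reversal at hour 4, reactions during the infusion, or most of the PB2452 concentration curve. Antibody that could have done so was there before dosing. Exclusion criterion 11 bars prior PB2452, so such antibody is pre-existing. Protocol 2.1.4 shows that this was common in Phase 1: "15 (31%) had been positive before they received PB2452 and 6 (12%) became positive after they received PB2452".

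No planned table relates pre-dose status to any outcome. Pre-dose results enter only the 2-fold rule, the by-visit summary and the listing. If the split is run, a finding of no difference by ADA status for Day 1 outcomes could be taken as reassurance about subjects with pre-existing antibody, and it would be weaker evidence on that question than it appears.

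**Working it through.** **Plan's own figure.** The documents give no figure for the ADA split. Their one design figure, power above 99% for the primary comparison, reproduces: 150 v 50, difference 15, SD 20, two-sided 0.05 gives 99.55% (noncentral t, 198 df). This point does not affect it.

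**Inputs (Protocol 2.1.4, Phase 1).** PB2452 arm, n = 48: 21 positive after exposure, of whom 15 pre-existing and 6 new, leaving 27 negative. Placebo arm, n = 16: 2 pre-existing. These rates are assumed to carry over from ages 18-50 to 50-80.

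**Measure.** Share of the true contrast retained = (proportion with antibody at dosing in the ADA-positive group) − (the same proportion in the ADA-negative group). A split by pre-dose status retains 100%. Antibody is treated as present or absent, regardless of titer.

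**Reading A: every pre-dose positive counts as positive.**
- PB2452 counts: 15/21 − 0/27 = 0.71.
- Pooled pre-existing rate p = 17/64 = 0.266, new-positive rate among pre-dose negatives e = 6/33 = 0.182: p / (p + (1 − p)e) = 0.266/0.399 = 0.67.
- With about 47 pre-dose positive subjects of 150, a new-positive rate of 5% of the arm gives 47/54.5 = 0.86, and 30% gives 47/92 = 0.51.

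**Reading B: pre-dose positives count only if boosted 2-fold.** Let b be the boosted share, which no document gives. Retained = 15b/(6 + 15b) − 15(1 − b)/(27 + 15(1 − b)).

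| b | positive group | negative group | retained |
|---|---|---|---|
| 1 | 15/21 = 0.714 | 0 | 0.71 |
| 0.75 | 11.25/17.25 = 0.652 | 3.75/30.75 = 0.122 | 0.53 |
| 0.50 | 7.5/13.5 = 0.556 | 7.5/34.5 = 0.217 | 0.34 |
| 0.25 | 3.75/9.75 = 0.385 | 11.25/38.25 = 0.294 | 0.09 |
| 6/33 = 0.18 | 0.3125 | 0.3125 | 0 |
| 0 | 0 | 15/42 = 0.357 | −0.36 |

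**Scale in 150 PB2452 subjects.** PB2452-arm rates: 150 × 15/48 = 46.9 pre-dose positive and 150 × 6/48 = 18.8 newly positive. Pooled rate: 150 × 17/64 = 39.8 and (150 − 39.8) × 6/33 = 20.0.

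**PK.** Protocol 2.1.4.1 gives "half-life values ranging from 1.5 to 9.2 hours for the dose range 0.1 g to 1 g". Day 7 is 144 h after dosing. At the longest half-life, the time from end of infusion to the Day 7 sample is (144 − 16.2)/9.2 = 13.9 half-lives for 18 g and (144 − 24.2)/9.2 = 13.0 for 36 g. That half-life comes from 30-minute infusions without ticagrelor, so applying it to 18 g and 36 g is an assumption.

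**Illustration only.** Suppose pre-dose antibody truly shifted the endpoint by 10 points (no document supports this value), with SD 20. Normal-approximation power would be 81% for a pre-dose split (47 v 103) and 57% for the SAP split under reading A (66 v 84, with the mixture variance in the positive group).

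**The case against.** Nothing is committed. The SAP only allows the split; no test or conclusion depends on it, and no outcome-by-ADA table of any kind is firmly planned. The by-visit summary and the listing keep Day -3 and Day 1 results visible, and SAP 2 allows exploratory analyses it does not name, so a pre-dose split could be made later. There may also be nothing to dilute. Protocol 2.1.4 reports of Phase 1: "The presence of these antibodies had no observed effect on the safety or efficacy of PB2452". The six new positives had titers of only 40 or 160, and the ADA harm named in Protocol 2.1.5.1 concerns re-exposure: "Development of antibodies to PB2452 might pose issues with a subsequent dose of PB2452". Finally, the severe figures need reading B and an unsourced boosted share. The SAP's wording makes the 2-fold rule look additive, which favors reading A.

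Most of this stands as a limit on consequence. Reading B remains open, because under reading A the 2-fold sentence has little left to do; its figures are hypothetical, while 0.67 to 0.71 rests on document counts. It is also true that post-dose status suits AEs collected to Day 35±3 and may bear on the Day 7 and Day 35 PK samples. None of this makes conversion at Day 7 or Day 35 a sensible grouping for 4-hour PRU or PRI. A regrouping made after database lock would count as post hoc under SAP 2.

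**Conclusion.** The concern holds, with low consequence. If the optional split is run as defined, it would show roughly 67% to 71% of any effect of pre-dose antibody on Day 1 outcomes. Under the stricter reading it would show less, with a change of sign only if fewer than 18% of pre-dose carriers are boosted. This assumes that Phase 1 ADA rates carry over and that antibody acts the same at any titer. The primary analysis is untouched, and Phase 1 gives no sign that an effect exists. Post-dose status remains right for incidence and for later-onset AEs.

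**What to change.** Add to SAP 12: if results are reported by ADA status, 4-hour PRU/PRI, PB2452 PK and Day 1-3 AEs will be reported by pre-dose ADA status (positive or negative on the last sample before infusion), within arm where applicable; treatment-emergent or boosted ADA status will be used for incidence and later-onset AEs. This follows the SAP 6.1 baseline convention for non-efficacy measures and removes the ambiguity of the 2-fold rule for the Day 1-3 tables. A subject whose Day -3 and Day 1 results disagree can be flagged in the existing listing.

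The cost is one sentence, one grouping variable from samples already scheduled, and a few more exploratory tables.

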9.3.8 Immunogenicity Analysis

The PB2454 antibodies will be summarized by visit and treatment. A listing of subjects will also be provided.

If positive ADA is observed, results may be reported by ADA status for AEs, efficacy and pharmacokinetics.

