6. GENERAL ASPECTS OF THE STATISTICAL ANALYSIS

6.1. Key Definitions

The Study Day is the day relative to the date of treatment (Day 1). In other words,

$$\text{Study Day} = \text{Date} - \text{Date of treatment} + 1,$$

if Date is on or after Date of treatment; or

$$\text{Study Day} = \text{Date} - \text{Date of treatment},$$

if Date is before Date of dosing.

For efficacy endpoints, baseline values will be defined as the last value before ticagrelor is administered, which is expected to be on Day -2. The pre-treatment value is defined as the last value before study drug is administered, which is expected to be on Day 1 (up to 10 minutes prior to PB2452/placebo infusion). If Day 1 value is missing, the value prior to that will be used as pre-treatment.

For all other endpoints, unless otherwise specified, baseline is the last non-missing observation before exposure to study treatment PB2452 or placebo, which is expected to be the pre-study drug measurement on Day 1, or Screening if the Day 1 data are not available.

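### SAP section 12: the 2-fold titre rule has no effect as written, so pre-existing antibody still detected after dosing counts as ADA-positive even without a rise

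*SAP*

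**What the plan says.** SAP section 12 defines ADA status in three consecutive sentences.

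1. The general rule: "An ADA-positive subject is defined as a subject with at least one ADA-positive sample at any time during the treatment or follow-up observation period". It places no condition on status before treatment.
2. A rule for subjects with a positive pre-treatment sample, who are *also* positive "if the titer of at least one post-treatment ADA is elevated at least 2 folds of the titer in pre-treatment sample".
3. The remainder: "In all other cases, a subject is considered negative for ADA".

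Protocol 9.3.8 gives no definition. It says only that, if positive ADA is seen, "results may be reported by ADA status for AEs, efficacy and pharmacokinetics"; SAP section 12 repeats this. Both documents also plan antibody summaries by visit and treatment, and subject listings, whether or not ADA status is used.

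ADA samples are scheduled on Day -3, Day 1, Day 7 and Day 35. A note to the Protocol's schedule requires the Day 1 sample to be drawn before the infusion starts. The matching SAP footnote does not repeat that note. For non-efficacy endpoints, SAP 6.1 states that "baseline is the last non-missing observation before exposure to study treatment PB2452 or placebo".

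**The concern.** The second sentence is worded as an addition to the first, but everyone it describes is already inside the first. A threshold that the authors evidently meant to matter therefore does nothing. A subject who carried antibody into the study, and whose level did not rise, is classed with subjects who developed antibody or had it boosted by PB2452.

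If adverse events, efficacy or pharmacokinetics are then shown by ADA status, the positive group mixes unchanged pre-existing antibody with a response to the drug, and any association with that response is blurred. A programmer who tries to give the second sentence a purpose would also produce a different grouping from one who follows the text literally.

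**Working it through.** **Step 1: the five possible states.** *Pre* is the pre-treatment sample and *post* is any sample after infusion. A rise means a post titre at least 2 times the pre titre.

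| State | Sentence 1 alone | Sentences 1 to 3 as written | Corrected rule |
|---|---|---|---|
| pre negative, post negative | negative | negative | negative |
| pre negative, post positive | positive | positive | positive |
| pre positive, post negative | negative | negative | negative |
| pre positive, post positive, no rise | positive | positive | **negative** |
| pre positive, post positive, rise | positive | positive | positive |

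The second and third columns agree in all five rows, so the titre rule changes 0 of 5 states. The corrected rule moves exactly one state, the fourth.

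**Step 2: the same check on titres.** Take an assumed grid of negative, 20, 40, 80 and 160 for the pre-treatment, Day 7 and Day 35 samples. This gives 5 × 5 × 5 = 125 patterns.

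- Patterns made positive by the titre rule that the first sentence had not already captured: 0.
- Pre-positive patterns without a rise: 4 + 9 + 16 + 25 = 54, for pre titres of 20, 40, 80 and 160.
- Of these 54, the 4 that are negative at both later visits are ADA-negative. The other 54 − 4 = 50 are ADA-positive as written.

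These are counts of patterns, not expected frequencies.

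**Step 3: the extra visits.** Sampling after Day 35 depends on antibody being found at Day 35. Anyone who reaches those visits is already positive under the first sentence, so later samples do not give the titre rule any work either.

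**Step 4: scale, from Phase 1 (Protocol 2.1.4).** Of 48 PB2452 recipients, 21 were positive 7 and/or 28 days after exposure: "15 (31%) had been positive before they received PB2452 and 6 (12%) became positive after they received PB2452".

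- The printed figures reproduce: 21/48 = 43.75% (printed 44%), 15/48 = 31.25% (31%), 6/48 = 12.5% (12%), and 15 + 6 = 21.
- Share of post-dose positives that were already positive: 15/21 = 71.4%.
- Let b be the number of the 15 with a 2-fold rise, which is not reported. Under the corrected rule, 15 − b of the 21 leave the positive group and 6 + b of 48 remain.

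| b | Change class | Remain ADA-positive |
|---|---|---|
| 0 | 15 of 21 (71.4%) | 6/48 (12.5%) |
| 5 | 10 of 21 (47.6%) | 11/48 (22.9%) |
| 10 | 5 of 21 (23.8%) | 16/48 (33.3%) |
| 15 | 0 of 21 | 21/48 (43.75%) |

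In the placebo group of 16, "3 (19%) were positive for anti-drug antibodies, with 2 (12%) having preexisting antibodies". If all 3 were positive after dosing, 0 to 2 of the 3 would change class.

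**The case against.** **The text does not contradict itself.** A reader might infer that it does. Yet with *also* in the second sentence and a residual third sentence, every subject receives exactly one status, as the table shows. A conflict appears only if the second sentence is taken to govern all pre-treatment positives. A subject without a rise would then be positive by the first sentence and negative by the third. That is the only reading that gives the second sentence a purpose, but the words do not state it. This objection stands, and so the fault is described here as redundancy. By the same token the literal text is deterministic, and programmers would differ only if one departed from it.

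**Not all unboosted pre-existing antibody is classed positive.** This also stands. It must still be detected in a treatment or follow-up sample; a subject positive before and negative after is ADA-negative.

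**The baseline is adequate.** A reader might fault SAP 6.1 because it names a fallback, "or Screening if the Day 1 data are not available", at which no ADA sample is scheduled. That does not hold. The governing rule is the last non-missing value before exposure, and SAP section 13 likewise takes the value closest to, but before, first study treatment. If Day 1 is missing, both lead to Day -3.

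**The intended meaning can be guessed.** The schedule footnotes in both documents speak of treatment-emergent ADA, which suggests that the authors had the distinction in mind. Neither document defines the term or ties it to ADA status, so it does not repair the definition.

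**The consequence is small.** Reporting by ADA status is optional, and the by-visit summaries and listings still allow results before and after dosing to be compared. This is accepted.

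**Conclusion.** The point holds, at minor severity. As written, the 2-fold rule is inert, and pre-existing antibody that persists after dosing without a rise is counted as ADA-positive. No other section of the Protocol or SAP corrects this.

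The size cannot be fixed from the documents. On Phase 1 counts it lies between 0 and 15 of 21 PB2452 recipients positive after dosing, and between 0 and 2 of 3 on placebo; both ranges include no effect. Carrying these counts to this trial is an assumption: the Phase 1 subjects were aged 18 to 50, received 0.1 to 18 g, and in Cohorts 1 to 3 had no ticagrelor. What Phase 1 does show is that pre-existing antibody is common enough for the rule to matter.

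It would be wrong to infer that the immunogenicity data as a whole, or the efficacy conclusion, are compromised. The by-visit summaries, the listings and the primary analysis do not use ADA status.

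One loose end could widen the problem. The Day 1 ADA sample sits under the treatment columns of the schedule. If a programmer counted it as a treatment-period sample, even a subject positive only before dosing would become ADA-positive.

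**What to change.** Before database lock, amend SAP section 12 as follows.

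- **First sentence:** restrict it to subjects who are negative at the pre-treatment baseline and have at least one positive post-infusion sample.
- **Second sentence:** state that subjects positive at baseline are ADA-positive only if at least one post-infusion titre is at least 2 times the baseline titre. This keeps the SAP's own threshold.
- **Day 1 sample:** state that the pre-infusion Day 1 sample is the baseline and not a treatment-period sample.
- **Third sentence:** this can stand.

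Showing pre-existing antibody as its own row is optional. It would make the table easier to read, but it also relabels subjects who were positive before and negative after dosing, so two of the five states would differ from the present text and not one.

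The cost is two edited sentences and one clarification. All the samples needed are already scheduled, and no analysis other than the summaries by ADA status is touched. Making the change before unblinding avoids a post hoc choice of who counts as ADA-positive.
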